## Summary of Changes to Protocol from Previous Version

| ZELTIQ Part Number   | Protocol Version  | Date   |
|----------------------|---|--|
| 208103-01            | 2.0   | July 25, 2018  |
| Affected Section (s) | Summary of Revisions Made   | Rationale  |
| 2.1 and 2.2          | Added [REDACTED] applicator as an example of applicators.                                       | To provide example of appropriate applicator types for the study.                                    |
| 2.1 and 3.13         | Added 3-Week Follow-Up contact post each treatment visit.                                       | To monitor any ongoing side effects and observations from the treatments.                            |
| 3.7                  | Removed inclusion criterion C.  | To allow enrollment of participants with smaller treatment areas.                                    |
| 3.12.1               | Added the option of using a GelPad and liner, depending on the type of applicator used.         | Depending on the type of applicator used in the study, various device components may be required.    |
| 3.12.1 and 3.14      | Added the option of capturing thermal images of the treated area after completion of treatment. | To provide information regarding the cooling performance of the CoolSculpting system.                |
| 3.12.2               | Made Treatment Visit #2 optional.   | Depending on the aesthetic outcome from Treatment Visit #1, Treatment Visit #2 may not be necessary. |

## 1. Protocol Summary

|                     |   |
|---------------------|---|
| Title               | Non-Invasive Fat Reduction with Cryolipolysis for Jawline Contouring  |
| Design              | Prospective, non-randomized, interventional cohort  |
| Purpose             | The purpose of this study is to evaluate the safety and efficacy of non-invasive reduction of subcutaneous fat along the jawline with Cryolipolysis |
| Enrollment          | Up to forty-five (45) subjects  |
| Clinical Site       | Up to three (3) investigational sites   |
| Subject Population  | Healthy adult men and women with skin fold thickness of > 1 cm on or below the jawline, and who desire reduction of jawline fat.                    |
| Primary Endpoint    | [REDACTED]  |
|                     | [REDACTED]  |
| Secondary Endpoints | [REDACTED]  |
|                     | [REDACTED]  |
| Sponsor             | ZELTIQ, an Allergan Affiliate
[name]
[name]  |

## 2. Introduction

### 2.1. **Background**

Fat reduction and body contouring procedures, which include invasive, minimally-invasive, and non-invasive procedures, have become increasingly popular aesthetic procedures. Patients who are obese and do not have specific fat bulges but require significant fat reduction to achieve aesthetic results are candidates for invasive and minimally-invasive procedures, such as liposuction and laser-assisted liposuction. Although effective at reducing fat, these invasive and minimally-invasive procedures involve significant patient pain, expense, downtime, and the risks typically associated with surgical procedures. As a result, patients who do not require significant fat reduction to achieve meaningful aesthetic results typically seek non-invasive fat reduction and body contouring procedures to avoid the pain, expense, downtime, and surgical risks associated with invasive and minimally-invasive procedures.

ZELTIQ Aesthetics has developed and commercialized a technology to non-invasively reduce subcutaneous fat. The ZELTIQ technology utilizes the sensitivity of fat cells to cold injury in order to selectively eliminate subcutaneous fat tissue without affecting the skin or other surrounding tissues. Termed cryolipolysis, this technology enables a non-invasive alternative for subcutaneous fat reduction through cellular apoptosis. The ZELTIQ CoolSculpting System, which is cleared for use in the United States for an indication of fat layer reduction in the flanks, abdomen, thighs, bra fat, back fat, banana roll, submental area and upper arms through cold-assisted lipolysis, has been clinically proven to reduce fat bulges, allowing patients to achieve noticeable and measurable aesthetic results without the pain, expense, downtime, and risks associated with existing invasive and minimally-invasive procedures.

[REDACTED]. The purpose of this study is to further evaluate the safety and efficacy of non-invasive subcutaneous fat reduction along the jawline to provide a better aesthetic improvement to lower face contour. Anatomical areas along the mental region and mandible, such as submental area, submandibular area and jowls, will be treated using the ZELTIQ CoolSculpting System and an appropriate applicator (such as [REDACTED]).

[REDACTED]

[figure not shown]
[REDACTED]

[REDACTED]

a CoolMini or a [REDACTED] applicator) for fat layer reduction. In this study, subjects will receive up to 2 treatments at 6 weeks apart. [REDACTED]

[figure not shown]
[REDACTED] Subjects will be followed for 12 weeks after receiving final treatment. Follow-ups will be performed at the following time points: 1-week, 3-week, 6-weeks and 12-weeks post treatment. Final efficacy assessment will be performed at 12-weeks post 2nd treatment. **Figure 1** shows the overall study flow:

**Figure 1: Study Visit Flowchart.** All visits require subjects to return to the study site except for the 1-week and 3-week Follow-up phone/email.

[figure not shown]

\*Follow-up conducted remotely via phone call or email

## 2.2. *Device Description*

**Figure 2. CoolSculpting System Control Unit.**

**Figure 3: CoolMini Applicator.**

ZELTIQ P/N: [REDACTED]

Protocol Number: ZA17-004

This document and the contents hereof are considered proprietary and confidential information of ZELTIQ Aesthetics, Inc. Disclosure to unauthorized individuals or dissemination, publication or copying is prohibited without prior written consent of ZELTIQ.

## 2.3. **Regulatory Status**

In Canada, the ZELTIQ CoolSculpting System is licensed ([REDACTED]) and approved for:

- Fat layer reduction through cold-assisted lipolysis
- Minimizing pain and thermal injury during laser and dermatological treatments
- Acting as a local anesthetic for procedures that induce minor local discomfort

The ZELTIQ system can also provide localized thermal therapy (hot or cold) to minimize pain for post-traumatic and/or post-surgical pain and to temporarily relieve minor aches and pains and muscle spasms. The optional massage function can also be used for temporary:

- Relief of minor muscle aches, pain and spasm
- Improvement in local circulation
- The CoolSculpting System also received Health Canada approval in September 2015 for colder temperatures and shorter treatment times.

## 3. Study Protocol

### 3.1. **Design**

Prospective, non-randomized interventional cohort.

### 3.2. **Study Duration**

Enrollment and follow-up is expected to take up to six (6) months for each subject.

### 3.3. **Physician Participants**

Study investigators must be practicing medical physicians with experience in the use of the ZELTIQ CoolSculpting System.

### 3.4. **Site Requirements**

Site investigators should have at least one study coordinator with experience in conducting clinical research and with sufficient time to conduct the study.

### 3.5. **Subject Recruitment**

Subjects who seek reduction of fat in the submental area, submandibular area or jowls will be recruited from the general population.

### 3.6. **Sample Size**

A maximum of forty-five (45) subjects will be treated at up to three investigational sites.

### 3.7. **Subject Eligibility**

To be eligible to participate in the study, subjects must meet all of the inclusion criteria and none of the exclusion criteria listed in **Table 1**.

**Table 1. Eligibility criteria.**

#### **Inclusion Criteria**

- a) Male or female subjects  $\geq 22$  years of age and  $\leq 65$  years of age.
- b) Treatment area skin fold thickness  $> 1\text{cm}$  (measured by caliper).
- c) No weight change exceeding 5% of body weight in the preceding month.
- d) Agreement to maintain his/her weight (i.e., within 5%) by not making any major changes in diet or exercise routine during the course of the study.
- e) Subject has signed a written informed consent form.

#### **Exclusion Criteria**

- a) Excessive skin laxity in the treatment area for which reduction of subcutaneous fat may, in the opinion of the investigator, result in an unacceptable aesthetic result.
- b) Prominent platysmal bands at rest which may interfere with assessment of treatment area.
- c) Evidence of any cause of enlargement in the treatment area other than localized subcutaneous fat, such as swollen lymph nodes or ptotic submandibular glands.
- d) Significant enlargement on the anterior neck that may prevent the proper placement of the applicator e.g. enlarged thyroid glands.
- e) Treatment with dermal fillers, chemical peels, radiofrequency or laser procedures that may affect contour in the treatment area within the past 6 months.
- f) Botulinum toxin, deoxycholic acid, or other aesthetic drug injections within the treatment area in the past 6 months.
- g) History of facial nerve paresis or paralysis (such as Bell's palsy).
- h) History of a fat reduction procedure (e.g., liposuction, surgery, lipolytic agents, etc.) or implant in or adjacent to the area of intended treatment.
- i) History of prior neck surgery, or prior surgery in the area of intended treatment.
- j) Current infection in and adjacent to treatment area.
- k) Known history of cryoglobulinemia, cold urticaria, cold agglutinin disease or paroxysmal cold hemoglobinuria.
- l) Known history of Raynaud's disease, or any known condition with a response to cold exposure that limits blood flow to the skin.

- m) History of bleeding disorder or is taking any medication that in the investigator's opinion may increase the subject's risk of bruising.
- n) Currently taking or has taken diet pills or weight control supplements within the past month.
- o) Any dermatological conditions, such as scars in the location of the treatment area that may interfere with the treatment or evaluation.
- p) Active implanted device such as a pacemaker, defibrillator, or drug delivery system.
- q) Pregnant or intending to become pregnant in the next 6 months.
- r) Lactating or has been lactating in the past 6 months.
- s) Unable or unwilling to comply with the study requirements.
- t) Currently enrolled in a clinical study of an unapproved investigational drug or device.
- u) Any other condition or laboratory value that would, in the professional opinion of the investigator, potentially affect the subject's response or the integrity of the data or would pose an unacceptable risk to the subject.

### **3.8. Informed Consent**

Study candidates shall receive an explanation of the study objectives, possible risks and benefits of the study, and be given adequate time to read the information included in the informed consent document. Candidates will be given an opportunity to ask questions about any of the information contained in the informed consent. Candidates must verbally acknowledge understanding of the informed consent, and sign the consent form accordingly. This form must have prior approval of the Institutional Review Board (IRB).

### **3.9. Screening Procedures**

#### **Screening Visit; Required; Day -45 to Day 0**

The subject shall be consented for study participation as described in Section 3.8. After the informed consent is signed, subjects will be screened for eligibility. Each subject will be evaluated to determine that all eligibility criteria are met. The investigator or designee shall complete a brief medical history and examine the subject to confirm eligibility for the study.

1. Obtain height and weight
2. Visually assess and palpate the intended treatment area to determine if it is appropriate for treatment.
3. Measure the skin fold thickness of the intended treatment areas using a caliper.
4. Assess for dermatological conditions that may lead to exclusion of a subject from the study.

5. Document potential candidate's medication use (including over-the-counter medications, vitamins and herbs), Fitzpatrick Skin Type, race and ethnicity as well as any skin irregularities (e.g. moles, birth marks, scars, stretch marks, discoloration) at the intended treatment area.

All female subjects of childbearing potential will be assessed for the start date of their last menstrual cycle to determine if they may be pregnant. If unsure, a pregnancy test (urine) may be taken at the screening visit. If the subject is pregnant, she will be excluded from participation. Subjects will also be advised to avoid becoming pregnant during the course of the study by using a medically accepted form of contraception if they are sexually active. If the subject becomes pregnant during the course of the study, she will not be treated subsequently with the study device or be required to have follow-up photographs or ultrasound measurements taken.

All subjects will be asked to maintain their weight by not making any major changes to their diet or exercise regimen during the course of the study. If a subject's weight change is more than 5% at 12 weeks after the last treatment, the subjects' data will be excluded from the primary effectiveness analyses. Subjects who do not maintain their weight within 5% will continue in the study, however their data will be excluded from efficacy analyses.

Subjects who meet all of the inclusion criteria and none of the exclusion criteria shall be eligible to participate in the study and the first treatment will be scheduled.

### **3.10. Study Enrollment**

Study Candidates who sign the informed consent, meet eligibility criteria and undergo initiation of study treatment are considered enrolled. Study treatment initiation is defined as the initiation of the cooling cycle after the placement of the applicator on the intended treatment area on the scheduled treatment day.

### **3.11. Study Photography**

Study candidates who sign the informed consent and meet eligibility criteria will be required to have baseline photographs of the intended treatment area taken. Baseline photographs will be taken using a standardized system prior to receiving the first treatment, and may also have additional photographs taken at subsequent treatment visits. All subjects will return 12 weeks after final treatment to have photographs of the treated area taken before exiting the study, using the same system and setup as baseline photographs.

### 3.12. *Study Treatment Procedures*

#### 3.12.1. **Treatment Visit #1; Required: Day 0**

1. All female subjects of childbearing potential will be asked to take a pregnancy test (urine) at the treatment visit. Exclude subject from participation if the results are positive.
2. Review and verify the subject continues to meet all eligibility criteria.
3. Obtain weight.
4. Obtain baseline standardized photographs using standardized setup and settings. In addition, 3-dimensional image may be captured.  
[REDACTED]

1. Clean the applicator per instructions in the Addendum to the User Manual.
8. Per Investigator's discretion, perform up to four additional cooling cycles to cover the intended treatment area [REDACTED] cycles per treatment visit). For additional cooling cycles, repeat Step 7 in Section 3.12.1
9. The need for post-treatment care is not expected for this study. Subjects will be encouraged to call the study site if they experience any unexpected effects (e.g., severe discomfort, severe and/or prolonged erythema, bruising, swelling; blistering, etc.) which may be related to the study.

### **3.12.2. Treatment Visit #2; Optional: Week 6 post-Treatment #1 ( $\pm$ 1 week)**

Per the Investigator's discretion, subjects may receive a second treatment (up to 5 cooling cycles) after completion of the 6-week post-Treatment #1 follow-up evaluation.

1. All female subjects of childbearing potential will be asked to take a pregnancy test (urine) at the treatment visit. Exclude subject from participation if the results are positive.
2. Review and verify the subject continues to meet all eligibility criteria.
3. Obtain standardized photographs and 3-dimensional images (optional).
4. Measure fat layer thickness of the treatment area with a commercially-available ultrasound device using a standardized protocol (optional).
5. Perform treatment as described in Section 3.12.1., #6-9.

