#### As-Treated Population (AT):

This population consists of all treated subjects regardless of whether they become pregnant or undergo weight change during the study.

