**Safety Population (SA):**

This population will consist of all treated subjects with safety evaluation after the treatment. This population should be identical to the AT population. The safety data analyses will be performed based on the Safety Population.

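### The pregnancy instruction at Treatment Visit #2 (3.12.2 step 1), read literally, is at odds with the in-study pregnancy rule in 3.9 and could cost a treated subject her 12-week safety evaluation

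*Combined protocol and SAP*

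**What the plan says.** The protocol deals with pregnancy at four points.

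- **Screening (3.9):** "If the subject is pregnant, she will be excluded from participation". The subject has not been treated.
- **Day 0 (3.12.1 step 1):** a urine test precedes the first cooling cycle, with an instruction to exclude if positive. She is still untreated.
- **Treatment Visit #2 (3.12.2 step 1):** the same test and the same instruction, "Exclude subject from participation if the results are positive". This visit comes "after completion of the 6-week post-Treatment #1 follow-up evaluation".
- **Pregnancy arising during the study (3.9):** "she will not be treated subsequently with the study device or be required to have follow-up photographs or ultrasound measurements taken".

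Three other places bear on her status. Under 3.10, eligible candidates who have consented and who "undergo initiation of study treatment are considered enrolled", so she is enrolled from the first cooling cycle. Section 3.13.4 requires a 12-week evaluation (±14 days) timed from the final treatment. In 3.16.2 the As-Treated population is "all treated subjects regardless of whether they become pregnant or undergo weight change during the study", and of the Safety population the plan says "This population should be identical to the AT population".

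**The concern.** At screening and on Day 0, exclusion from participation keeps an untreated woman out of the study. At Visit #2 the same words are applied to a woman who has had Treatment #1 and completed her 6-week evaluation. Taken literally, they remove her from the study; 3.9 only stops further treatment and waives two imaging items. Section 3.12.2 neither limits the instruction to the second treatment nor refers to 3.9.

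Table 2 makes the literal reading easier to fall into. It schedules pregnancy tests only at screening, Visit #1 and Visit #2, so Visit #2 is the only scheduled test after exposure and the point at which the 3.9 rule is most likely to be needed. The table also shows the 12-week column under the heading for the second treatment, so it does not prompt that visit for a woman who had only one.

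At stake is the final required safety examination of a subject who has been exposed to the device and is pregnant.

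**Working it through.** The plan states no figure to reproduce. The check is a comparison of rules, followed by a count of what the literal reading would remove.

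**1. Which rule do the other sections support?**

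- Section 3.9 waives only photographs and ultrasound. It does not waive weight, clinical examination, adverse event assessment or the questionnaire.
- In Table 2, follow-up photographs and ultrasound are optional at the 6-week visits and required only at 12 weeks. A waiver of required follow-up images therefore has practical effect only if she is still in the study at 12 weeks.
- Section 3.13.4 times the 12-week evaluation from the final treatment. With no second treatment, that is Treatment #1.
- The As-Treated population keeps treated subjects who become pregnant.

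All four point to retention for safety follow-up.

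**2. Scheduled time lost if 3.12.2 is followed literally** (weeks after Treatment #1)

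- Stop at Visit #2: week 6 ± 1, so weeks 5 to 7.
- Required final evaluation: week 12 ± 2, so weeks 10 to 14.
- Nominal loss: 12 − 6 = 6 weeks.
- Shortest: 10 − 7 = 3 weeks. Longest: 14 − 5 = 9 weeks.

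**3. Contacts and items lost**

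- With one treatment the scheduled contacts are weeks 1 and 3 (remote) and weeks 6 and 12 (in person). Lost: 1 of 4 contacts and 1 of 2 in-person examinations.
- Section 3.13.4 lists 9 items. Section 3.9 waives 2 (photographs, ultrasound), leaving 9 − 2 = 7 due: weight, the questionnaire and 5 safety items (skin and tissue findings; sensation and pain; dry mouth; motor nerve function; adverse events).

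**4. Late-onset risk**

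Section 7.2 places paradoxical hyperplasia at 2 to 5 months. At 4.348 weeks per month this is 2 × 4.348 = 8.7 to 5 × 4.348 = 21.7 weeks, a span of 13.0 weeks. The 6-week visit (weeks 5 to 7) is outside the window and the 12-week visit (weeks 10 to 14) is inside it. The part of the window that the literal reading removes is 10 − 8.7 = 1.3 to 14 − 8.7 = 5.3 weeks.

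**5. How often**

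The documents give neither the number of women of childbearing potential nor a pregnancy rate. Assuming 20 to 35 such women and 0.2% to 1% pregnant by week 6, the expected number is 20 × 0.002 = 0.04 to 35 × 0.01 = 0.35. Treatment #2 is optional, and this test is taken only by women who go forward to it, so the true expectation is lower.

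**The case against.** The strongest reply is that 3.9 already covers this case. It has a rule written for pregnancy during the study. Step 1 of 3.12.2 sits under treatment procedures and acts as a gate to a treatment, so *exclude* can be read as *do not re-treat*. On that reading the sections agree and nothing is lost. This stands as a possible reading, and it is the one the rest of the protocol supports. It does not remove the point, because 3.12.2 does not say so, and the same words mean full exclusion in their two other uses.

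There are partial safeguards: weekly calls while reported symptoms are unresolved (3.13.1, 3.13.2) and optional visits (3.13.5). They apply only if the site still regards her as a participant. The calls depend on her having reported something and cannot replace the oral and motor nerve examination; the extent of an optional visit is left to the investigator.

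Several stronger readings are tempting, and the documents do not support them.

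- *That the eligibility re-check in step 2 leaves a pregnant subject with no stated consequence.* Section 3.9 states one.
- *That 3.11 independently requires her 12-week return.* It concerns a return for photographs, which 3.9 says she need not have.
- *That the safety endpoint in 3.14.1 fixes a 12-week assessment for her.* It is timed from the second treatment, which she does not receive.
- *That this sentence accounts for the gap in observing paradoxical hyperplasia.* A compliant one-treatment subject leaves at weeks 10 to 14, so 21.7 − 14 = 7.7 to 21.7 − 10 = 11.7 of the 13.0 weeks have no required visit for her either. Most of that gap belongs to the general design.

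**Conclusion.** The point holds as a minor one. Read literally, 3.12.2 step 1 is at odds with the in-study pregnancy rule in 3.9, and with 3.13.4 and the As-Treated definition. A reader might infer that the two rules cannot be reconciled or that follow-up will be lost. Neither follows: the loss is possible, not certain, and depends on how a site reads one word.

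If the instruction is followed literally, the cost per affected subject is nominally 6 weeks of scheduled observation (range 3 to 9) and the second of two in-person post-treatment examinations, with its 5 safety items. If it is read as no further treatment, the cost is nil.

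Under the assumptions above, fewer than one subject is expected to be affected, and most likely none. She stays in the As-Treated population under either reading, and in the Safety population through her earlier evaluations. The effect on summary statistics is negligible. The reason to change the sentence is safety follow-up of an exposed subject.

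**What to change.** Replace the exclusion sentence in 3.12.2 step 1 with: *If positive, do not give Treatment #2; the subject remains in the study for safety follow-up through 12 weeks after her last treatment, with photographs and ultrasound not required (see 3.9).*

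Limit this to an actual positive test or a confirmed pregnancy. Exclusion criterion q also covers a subject who only intends to become pregnant. Section 3.9 does not waive her images, and extending the waiver to her would lose 12-week photographs and ultrasound that the efficacy analyses need. Leave the Day 0 step in 3.12.1 unchanged, since there the subject is not yet treated.

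The cost is one sentence. It adds no visit beyond those 3.13.4 already requires and changes no analysis.
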